Patient-reported outcomes (EORTC QLQ-C30 and EORTC QLQ-OV28 questionnaires)	-7 to 0 (+1 day)	Every eight weeks from randomization				•	-				

Assessments and procedures	Screening* (days before first drug infusion)	Treatment						End of treatment (EOT) †	Follow-up		
		Cycle 1		Cycle 2**		Further cycles**					
		D1	D8	D1	D8	D1	D8				
Concomitant therapies	-14 to 0	Throughout the "on-treatment period"***						-			
Adverse events	- §	Throughout the "on-treatment period"***						• (11)			

Regardless of the treatment administered, the same schedule of assessments will apply.

* Screening procedures will have to be repeated in case that the first infusion of the study treatment is given out of the established windows. **Note: Randomization of patients should occur as close in time as possible to the administration of the first dose of study drug.**

**Further treatment cycles will be administered every three weeks (\pm 48 hours) for PM01183 (Arm A) and topotecan (Arm B), or every four weeks (\pm 48 hours) for PLD (Arm B) if the patient fulfills all re-treatment criteria.

***"On treatment period" = from first infusion of the study treatment (PM01183, PLD or topotecan) to EOT [30 days after the day of the last dose administration, unless the patient starts a new antitumor therapy or dies (whichever occurs first), in which case the date of administration of this new therapy or the date of death will be considered the date of end of treatment].

† At 30 \pm 7 days after the last treatment infusion, an EOT should be performed. The listed assessments will have to be done if no recent data are available (i.e. within last 10 days prior to the EOT visit) or if the last data available show a grade \geq 2 treatment-related alteration whenever the medical condition of the patient may allow these evaluations.

§ Only information on SAEs that occur after signature of informed consent form is required. Grading should be as per NCI-CTCAE v. 4.

Time windows for Cycle 2 and further: a 3-day window will be allowed for laboratory tests and ECG, a 1-week window for tumor assessments as per RECIST v.1.1, tumor marker evaluation and patient-reported outcomes, a 1-day window for clinical assessments (ECOG PS, vital signs, weight, BSA, etc.), a 7-day window for the assessments at EOT, and a 2-week window for the follow-up period.

1. Height to be measured at baseline only.

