5.4 PRE-TREATMENT ASSESSMENTS

During the pre-treatment period, following signature of the ICF, the Investigator will confirm the patient's eligibility for the study by conducting the assessments summarized in [Table 5](#).

Table 5. Screening period: pre-treatment assessments.

	ASSESSMENT	TIME
1. Written informed consent (general and pharmacogenetic and PGx sub-study)		Before any study procedures.
2. Medical and cancer history/ clinical examination	♦ Demographic data.	Within 28 days prior to first infusion.
	♦ Medical and cancer history/baseline condition: 
 ◦ Primary diagnosis. ◦ Prior treatments (with best response and TTP, when available). ◦ Documented date of relapse. ♦ Disease-related signs and symptoms. ♦ Complete physical examination, including weight, height and calculation of BSA. ♦ Concomitant therapies. 	Within 14 days prior to first infusion.*/**
	♦ Performance status (ECOG PS).	Within 7 days prior to first infusion.*
	♦ Vital signs: heart rate, blood pressure and body temperature.	
3. Laboratory tests	♦ Hematology: differential WBC counts (including neutrophil, lymphocyte and monocyte counts), platelet count and hemoglobin. ♦ Biochemistry: Liver function test (ALT, AST, AP, GGT, total bilirubin; direct bilirubin only if total bilirubin is abnormally high); total proteins, albumin, creatinine, CPK, glucose, calculated CrCL (as per Cockcroft and Gault's formula), and serum electrolytes (Na ⁺ , K ⁺ , Cl ⁻).	Within 7 days prior to first infusion.***
4. Pregnancy test (if women of childbearing potential)	Assessment of β-hCG (urine or serum).	Within 7 days prior to first infusion, if applicable.***
5. ECG	Cardiac rhythm will be identified in ECG intervals of at least 30 seconds of duration, PR interval, QT interval (raw), heart rate and QRS complex.	Within 7 days prior to first infusion.***
6. LVEF	ECHO or MUGA.	Within 14 days prior to first infusion.****
7. PGx	Available stored paraffin-embedded tumor tissue samples; only in those patients that give their written informed consent for the PGx sub-study.	-

	ASSESSMENT	TIME
8. Radiological tumor assessment	Contrast enhanced helical CT-scan or MRI, as clinically relevant.	Within 14 days prior to first infusion.***
9. Tumor marker evaluation	CA-125.	Within 7 days prior to first infusion.***
10. Patient-reported outcomes	EORTC QLQ-C30 and EORTC QLQ-OV28 questionnaires.	Within 7 days prior to first infusion.*

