5.8 EVALUATIONS AT END OF TREATMENT

The *end-of-treatment visit* will be scheduled within 30 days (\pm 7 days) after the last treatment infusion, unless the patient starts any subsequent antitumor therapy, in which case the end-of-treatment visit should be performed immediately before the start of the new therapy (ideally the day before or the same day).

Patients, regardless of the reason for ending the treatment, will have to undergo at the end of treatment the following assessments:

- ECOG PS.
- Concomitant therapies.
- Laboratory tests (hematology and biochemistry).
- Pregnancy test (if applicable).
- ECG (if clinically indicated).
- LVEF by ECHO or MUGA (if clinically indicated).
- Radiological tumor assessment (only in those patients who discontinue treatment without radiological PD when the end-of-treatment visit coincides with the planned every-eight-weeks evaluation schedule).
- Tumor marker (CA-125) evaluation, if baseline levels were higher than normal.
- Patient-reported outcomes (EORTC QLQ-C30 and EORTC QLQ-OV28 questionnaires).
- Adverse events.

All these evaluations will only have to be repeated for those parameters for which no measurement is available within 10 days before the end-of-treatment visit, or for those parameters with values that were out of range in the last assessment (grade \geq 2 according to NCI-CTCAE v.4) and considered as treatment-related whenever the medical condition of the patient may allow these evaluations.

Adverse events must be reported for 30 days after the last study treatment administration. All serious adverse events (SAEs) occurring within 30 days of the last study treatment administration or until the start of a new antitumor therapy, whichever occurs first, will be reported. Beyond this period of time, only those suspected to be treatment-related SAEs will be reported (Section [7.4.2](#)).

The Sponsor will evaluate all safety information that is spontaneously reported by an Investigator beyond the time frame specified in the protocol.

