8.4 Patient-reported Outcomes (PRO)

To measure the quality of life of patients, EORTC QLQ-C30 and EORTC QLQ-OV28 questionnaires will be analyzed every eight weeks from randomization and while on treatment.

PRO will be analyzed by means of longitudinal modelling and T-test comparisons to determine if efficacy and side effects are accompanied by measurable changes. The analysis will be performed on summary scores of EORTC QLQ-C30 and EORTC QLQ-OV28 questionnaires, as well as on subscales and individual symptoms.

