12.8 PRO at treatment

Completion rate is defined as the number of patients with answer to item X in the numerator and the number of patients on treatment in each time point as denominator.

Missing data will not be taken into account in the analyses; anyway, if the quantity is considered relevant then supportive analyses will be performed applying a conservative approach of assuming missing data as failures.

Table 12.8.1 Completion rate

Item	Cycle	PM01183		Control	
		Missing (%)	Completed (%)	Missing (%)	Completed (%)
EORTC QLQ-C30					
Item 1	Baseline				
	Week 6				
	...				
....	Baseline				
	...				
Any item	Baseline				
	Week 6				
	...				
EORTC QLQ-OV28					
Item 31	Baseline				
	Week 6				
	...				
....	Baseline				
	...				
Any item	Baseline				
	Week 6				
	...				
EORTC QLQ-C30 and QLQ-OV28					
Any item	Baseline				
	...				

Table 12.8.2 T-test change vs. baseline

Item	Cycle	PM01183		Control*		p-value
		N	Mean (std)	N	Mean (std)	
*Control refers to PLD and/or topotecan						
Item 1	Week 6					
	Week 12					
	...					
....	Week 6					
	Week 12					
	...					
Item 58	Week 6					
	Week 12					
	...					
*Control refers to PLD						
Item 1	Week 6					
	Week 12					
	...					
....	Week 6					
	Week 12					
	...					
Item 58	Week 6					
	Week 12					
	...					
*Control refers to topotecan						
Item 1	Week 6					
	Week 12					
	...					
....	Week 6					
	Week 12					
	...					
Item 58	Week 6					
	Week 12					
	...					

Table 12.8.3 Percentage of patients with an improvement $\geq 10\%$ vs. baseline

Item	Cycle	PM01183		Control*		p-value
		N	%	N	%	
*Control refers to PLD and/or topotecan						
Item 1	Week 6					
	Week 12					
	...					
....	Week 6					
	Week 12					
	...					

[figure not shown]
Item	Cycle	PM01183		Control*		p-value
		N	%	N	%	
Item 58	Week 6					
	Week 12					
	...					
*Control refers to PLD						
Item 1	Week 6					
	Week 12					
	...					
....	Week 6					
	Week 12					
	...					
Item 58	Week 6					
	Week 12					
	...					
*Control refers to topotecan						
Item 1	Week 6					
	Week 12					
	...					
....	Week 6					
	Week 12					
	...					
Item 58	Week 6					
	Week 12					
	...					

Longitudinal analyses will be performed assuming a mixed-effect model with treatment (Y), time effect (days after baseline), and a time-treatment interaction as covariates, using a covariance structure of autoregressive order 1.

Table 12.8.4 Mixed effect model

Item	Estimated point change per day	p-value	Mean change during treatment

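### The quality-of-life mixed model tests a slope but names only an AR(1) covariance, so its standard error may be too small if patients' slopes vary and too large if patients differ only in level

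*SAP*

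**What the plan says.** SAP 8.4 plans longitudinal modelling and t-tests for the EORTC QLQ-C30 and QLQ-OV28. SAP 12.8 gives the model: treatment, time in days after baseline, "and a time-treatment interaction as covariates, using a covariance structure of autoregressive order 1". It is called a mixed-effect model, but no random intercept or random slope is named. No robust standard error, alternative structure or rule for choosing one is given. Table 12.8.4 reports an estimated change per day, a p-value and a mean change for items 1 to 58, under three definitions of control.

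On timing, SAP 8.4 says the "questionnaires will be analyzed every eight weeks from randomization and while on treatment". The notes to the Protocol Schedule of Assessments allow "a 1-week window for tumor assessments as per RECIST v.1.1, tumor marker evaluation and patient-reported outcomes". Protocol 5.8 adds a questionnaire at the end-of-treatment visit, but only for parameters "for which no measurement is available within 10 days before the end-of-treatment visit". Visits are therefore equally spaced by plan. In practice they vary within the window, and the end-of-treatment questionnaire can fall off the 8-week grid.

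**The concern.** The tested quantity is a difference in slopes. Its standard error depends on how much individual patients' slopes vary, and AR(1) has no term for that. AR(1) assumes one variance at all times and a correlation that decays with each step between records. Two plausible departures push the standard error in opposite directions:

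- If patients improve or worsen at different rates, AR(1) understates the uncertainty of the slope difference, and the test rejects too often.
- If patients differ by a stable amount and correlation does not decay, AR(1) overstates it, and the test loses sensitivity.

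Every p-value in Table 12.8.4 depends on this choice, and the SAP has no step that would reveal a poor fit. Patient-reported outcomes are a secondary objective (SAP 4.2).

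**Working it through.** The plan states no sample size, SD, correlation or alpha for this model, so there is no figure of its own to reproduce. The check is by simulation.

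**Why the covariance matters.** Let t be time in 8-week units, with patient intercept SD s0, slope SD s1 (taken as independent) and residual SD se.

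- Variance at t: s0² + s1²t² + se². Covariance between t and u: s0² + s1²tu.
- With s0 = 17, se = 14 and s1 = 0, the variance is 289 + 196 = 485 (SD 22.0) and the correlation is 289/485 = 0.60 at every lag. AR(1) with the same lag-1 value gives 0.60, 0.36 and 0.22 at lags 1, 2 and 3.
- With s1 = 4, the variance at week 32 (t = 4) is 485 + 16 × 16 = 741 (SD 27.2). AR(1) holds it constant.

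**Inputs from the documents.** 420 patients randomized 1:1; control median PFS 3.5 months and HR 0.7 (SAP 5.2), used as time on treatment; questionnaires every 56 days with the 1-week window read as ±7 days; an end-of-treatment questionnaire.

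**Inputs assumed.** Exponential time on treatment capped at about 71 weeks; end-of-treatment questionnaire 0–30 days after stopping; total SD about 22 before slope variation; correlation 0.6–0.8; slope SD 0–6 points per 8 weeks; dropout unrelated to the scores; no true treatment-by-time effect. Error rates depend only on ratios of these SDs. Slope SD 4 is 4/14 = 0.29 residual SDs per 8 weeks.

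**Method.** 500 trials per scenario, REML, two-sided 5% test of the interaction. The Monte Carlo SE at 5% is √(0.05 × 0.95/500) = 1.0 point. SE ratio means model SE divided by empirical SE.

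| True data | Visits | Plain AR(1): type I (SE ratio) | Random intercept + AR(1): type I | Random intercept and slope: type I |
|---|---|---|---|---|
| AR(1), ρ 0.6 | equal | 4.6% (1.06) | 5.2% | 3.8% |
| Serial, ρ 0.6 | uneven | 5.6% (0.95) | 6.8% | 6.4% |
| Serial, ρ 0.8 | uneven | 6.4% (0.94) | 7.8% | 6.0% |
| Level only | equal | 2.0% (1.17) | 4.2% | 3.6% |
| Level only | uneven | 2.0% (1.17) | 6.0% | 5.2% |
| Slope SD 2 | equal | 4.2% (1.03) | 10.2% | 4.2% |
| Slope SD 2 | uneven | 6.4% (0.96) | 16.0% | 6.2% |
| Slope SD 4 | equal | 9.8% (0.84) | 17.0% | 3.0% |
| Slope SD 4 | uneven | 15.0% (0.75) | 24.6% | 5.4% |
| Slope SD 6 | uneven | 21.4% (0.65) | 28.8% | 5.0% |

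**Role of spacing.** About 66% of simulated gaps fell within 49–63 days and 13% were below 42. The last gap had median 45 days (5–95%: 16–74). With serial correlation and uneven visits, plain AR(1) gave 5.6% and 6.4%, against 5.8% and 5.0% for a continuous-time power covariance, which handles the spacing correctly. With slope variation, the continuous-time structure was no better than plain AR(1): 15.2% at SD 4 and 20.4% at SD 6. The missing slope term therefore drives the error, not the indexing of visits.

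**Remedies.** Over the ten scenarios:

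- Random intercept and slope, model SE: type I 3.0–6.4%, SE ratio 0.96–1.07.
- The same model with sandwich SE: 3.2–7.0%, ratio 0.94–1.06.
- AR(1) with sandwich SE: 4.2–7.8%, ratio 0.94–1.05.

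**Sensitivity to the assumptions.** Two further runs of 250 trials per scenario agree.

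- One used ML, between-patient SD 15 and residual SD 12. It gave 2.8% with level differences only; 10–14% at slope SD 0.05–0.08 points per day (× 56 = 2.8–4.5 per 8 weeks); and 22% at 0.12 (6.7 per 8 weeks). Sandwich SEs gave 3–8%.
- The other gave about 4% with no slope variation (SE about 13% too large), 7% at SD 2 and 16–18% at SD 4–6 (SE 28–34% too small). Sandwich SEs gave 6–8%.

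**The case against.** **The spacing is not the cause.** A reader might infer that uneven visits invalidate AR(1). The documents plan equal 8-week visits, and unevenness alone left type I error at 5.6–6.4%. A reader might also infer that the end-of-treatment questionnaire comes months after the previous one. Questionnaires continue every 8 weeks on treatment, so such a gap would generally need a missed visit. The SAP also does not say whether that questionnaire enters the model. This objection stands.

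**Nothing shows that slopes differ.** A reader might conclude that the standard errors are wrong. No document states a slope variance, and at SD 2 plain AR(1) is near nominal. The supported statement is conditional: they may be wrong, in a direction set by the data. This also stands.

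**Mixed-effect may imply random effects.** A random intercept plus AR(1) is a fair reading, and it largely removes the too-large direction. It does not cure slope variation: type I error becomes 10.2–16.0% at SD 2, 17.0–24.6% at SD 4 and 28.8% at SD 6. The objection fails where false positives are concerned.

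**The analysis is descriptive.** Table 12.8.4 holds 58 × 3 = 174 p-values with no alpha allocated, and Tables 12.8.2 and 12.8.3 compare the arms without AR(1). This limits the consequence. It does not make a standard error that rests on one unchecked structure a good choice when the alternative is almost free.

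**Conclusion.** The point holds in conditional form. The SAP reports and tests a slope under AR(1) alone, and nothing in the plan protects the standard error if AR(1) fails.

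With uneven visits, the plain AR(1) test is near nominal at slope SD 2 points per 8 weeks (about 4–7%), about 15% at SD 4 and 18–21% at SD 6. If patients differ only in stable level, it is conservative (about 2–4%). These figures rest on assumed variances and on dropout unrelated to the scores; bias from informative dropout was not examined.

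The consequence is confined to a secondary patient-reported outcome analysis, and PFS is untouched. The change should be made, but it is not critical to the trial.

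**What to change.** In SAP 12.8, replace the AR(1) clause with a patient-level random intercept and random slope in days, and request empirical (sandwich) standard errors for the treatment-by-time test. State the fallback: if the random-slope model does not converge, keep AR(1) with empirical standard errors.

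Two alternatives are not recommended. A continuous-time power covariance alone leaves the slope problem in place. An unstructured matrix by scheduled visit has no natural slot for the off-grid end-of-treatment questionnaire.

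The cost is one SAP sentence and one changed SAS statement. No data collection, sample size or primary analysis changes.

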APPENDIX II

13 DB Listings

Database listings including key variables showing all the recorded information following CRF's Form name will be shown.

-Listing 13.1.1: Subject

Treatment arm	Patient id.	Country / Site number	Country	Investigator first name	Investigator last name	Institution	Address

-Listing 13.1.2: Visit Date

Treatment arm	Patient id.	Date of visit

-Listing 13.1.3: Screening

Treatment arm	Patient id.	Protocol version	Date of birth	Informed consent date	Planned date of treatment initiation	Histology	PFI	PS	#Regimens	Prior agents (Preference)	RECIST (Measurable)	ANC (10^9/L)	BSA	Subject met all eligibility requirements (If not, specify)	Is patient a screening failure	Screen failure date

-Listing 13.1.4: Randomization Details

Treatment arm	Patient id.	Ready to randomization?	Randomization ID	Date and time of randomization	Date of patient randomization in the study	Stratum name	PFI	PS	Prior chemotherapy	Actual treatment to be given	Now

-Listing 13.1.5: Study Registration

Treatment arm	Patient id.	Informed consent date	PGt/PGx consent	Date of PGt/PGx sample	Date of blood sample	Adequate contraception (If NA, specify)

-Listing 13.1.6: Demographics

Treatment arm	Patient id.	Date of birth	Age (years)	Is the patient of childbearing potential?	Race (Other, specify)	Estimated DOB

-Listing 13.1.7: Pregnancy Test

Treatment arm	Patient id.	Visit	Not done	Which type of test was performed?	Date of sample	Reason for clinically indicated repeat	Result

-Listing 13.1.8: Medical History

Treatment arm	Patient id.	Medical history	Description	Verbatim	Onset date	Resolved date	Ongoing?
---------------	-------------	-----------------	-------------	----------	------------	---------------	----------

MedDRA codes will be also added.

-Listing 13.1.9: Cancer History

-Listing 13.1.10: Prior Anticancer Therapy: Cytoreductive surgeries

Optimal/Suboptimal therapy by location of damage

-Listing 13.1.11: Prior AntiCancer Therapy: Other Surgical Procedures

Treatment arm	Patient id.	Prior surgery	Procedures	Date	Intention

-Listing 13.1.12: Prior AntiCancer Therapy: RadioTherapy

-Listing 13.1.13: Prior AntiCancer Medical Therapy for Study Disease

ATC codes will be also added

-Listing 13.1.14: Hematology

-Listing 13.1.15: Biochemistry

-Listing 13.1.16: Physical Examination

-Listing 13.1.17: Performance Status

Treatment arm	Patient id.	Visit	Not done	Date	PS (ECOG)
---------------	-------------	-------	----------	------	-----------

-Listing 13.1.18: Vital Signs

Treatment arm	Patient id.	Visit	Not done	Date	Heart rate	BPS	BPD	Temperature
---------------	-------------	-------	----------	------	------------	-----	-----	-------------

-Listing 13.1.19: Electrocardiogram

-Listing 13.1.20: Left Ventricular Ejection Fraction (LVEF)

Treatment arm	Patient id.	Visit	Not done	Date	Reason for clinically indicated	Method	LVEF (%)	Range (%)	Result	Abnormal, specify	LVEF (derived)
---------------	-------------	-------	----------	------	---------------------------------	--------	----------	-----------	--------	-------------------	----------------

-Listing 13.1.21: Anti-emetic Prophylactic Medication (Per Protocol)

ATC codes will be also added.

-Listing 13.1.22: CSF Prophylactic Medication

ATC codes will be also added.

-Listing 13.1.23: PM01183 Administration

-Listing 13.1.24: PM01183 Re-Administration

-Listing 13.1.25: Topotecan Administration

-Listing 13.1.26: Topotecan Re-Administration

-Listing 13.1.27: PLD Administration

-Listing 13.1.28: PLD Re-Administration

-Listing 13.1.29: Adverse Events YN?

Treatment arm					Patient id.				AEs			

-Listing 13.1.30: Adverse Events

Treatment arm	Patient id.	Adverse event	Grade	Start date (Ongoing)	End date (Duration/ongoing)	Relationship (PM1183/Topotecan/PLD/Specify)	Action	Serious Event (Death/Life Threat./Hospi./Disa./Conge./Other Impor./Infectious.)	Outcome	SAE associated to QC?	Case ID	Derived subject number

MedDRA codes will be also added.

-Listing 13.1.31: SAE summary

Treatment arm	Patient id.	Adverse event	Outcome	Start date	Case ID	Death	Life Threat.	Hospi.	Admission date	Discharge date	Disa.	Conge.	Other Medi.	Infec.	Narrative	Nulli.	Related docs?	Serious event	#Submi. to PHV

-Listing 13.1.32: SAE Attachments

Treatment arm					Patient id.				Attachment				

-Listing 13.1.33: Concomitant Medication YN?

Treatment arm					Patient id.				Concomitant medication?				

-Listing 13.1.34: Concomitant Medication

Treatment arm	Patient id.	Type of therapy	Drug name	Route	Dose	Unit	Frequency	No. of doses	No. of time units	Time units	Start date	End date	Ongoing	Reason	Indication	AEs	MH	Other, specify

ATC codes will be also added.

-Listing 13.1.35: Concomitant Procedures

Treatment arm	Patient id.	Not Done	Procedure	Indication	Date of Procedure	AE	MH	Result / Comments

MedDRA codes will be also added.

-Listing 13.1.36: Other tests/procedures

Treatment arm	Patient id.	Not done	Test name	Test date	Test result	Test unit

MedDRA codes will be also added.

-Listing 13.1.37: Target Lesions

Treatment arm	Patient id.	Were target lesions assessed	Target lesions	Lesion number	Organ	Specify	Lesion description	Date	Method (specify)	Longest diameter	Sum of diameters

-Listing 13.1.38: Non Target Lesions

Treatment arm	Patient id.	Were non target lesions assessed.	Non target lesions	Organ	Specify	Lesion description	Date	Method (specify)	Response

-Listing 13.1.39: New Lesions

Treatment arm	Patient id.	New lesions	Organ	Specify	Lesion description	Date	Method (specify)

-Listing 13.1.40: Radiological Evaluation of Response

Treatment arm	Patient id.	Evaluation (Not done)	Date	Target lesions	Non-Target lesions	New lesion	Not done	Overall cycle response

-Listing 13.1.41: Tumor Markers

Treatment arm	Patient id.	Not done	Date	CA125	Clinically indicated repeat	Age (Hidden)

-Listing 13.1.42: End of Treatment

Treatment arm	Patient id.	Reason	Specify (Investigator's decision)	Specify (AE)	Specify (Other)	Symptomatic deterioration date	Symptomatic deterioration, please specify

-Listing 13.1.43: Follow Up

Treatment arm	Patient id.	Date	Survival	Disease status	PD or any further therapy	TA done	TA not done	Specify (not done)

-Listing 13.1.44: Surgery procedures for Study Disease (after End of Treatment)

Treatment arm	Patient id.	Further surgery	Procedure	Date	Surgery Result

-Listing 13.1.45: Radiotherapy/Brachytherapy (after End of Treatment)

Treatment arm	Patient id.	Further radiotherapy	Site	Start date	End date	Ongoing	Total dose (Gy)

-Listing 13.1.46: Medical Treatment (after End of Treatment)

Treatment arm	Patient id.	Further therapy	Agent	Route	Start date	End date	Ongoing	Best response

ATC codes will be also added.

-Listing 13.1.47: Death Report Form

Treatment arm	Patient id.	Date	Cause	Specify (Other)	Autopsy	Attachment

-Listing 13.1.48: Off Study

Treatment arm	Patient id.	Off study	Date	Primary reason

-Listing 13.1.49: Pharmacokinetics

Treatment arm	Patient id.	PK samples	Sample No.	Day	Sampling time	Not done	Date	Actual time	Derived DateTime	Comments	Cycle the next Pharmacokinetics is due at:

-Listing 13.1.50: EORTC Quality of Life Questionnaire

Treatment arm	Patient id.	Not done	Date	Q1 to Q5	Specify if not performed	Q6 to Q28	Specify if not performed	Q29-Q30	Specify if not performed	Q31-Q54	Specify if not performed	Q55-Q56	Specify if not performed	Q57-Q58	Specify if not performed

-Listing 13.1.51: Treatment Continuation

Treatment arm	Patient id.	Add next cycle?

-Listing 13.1.52: Investigator Comments

Treatment arm	Patient id.	Visit	Form	Date	Comment

-Listing 13.1.53: Unscheduled

Treatment arm	Patient id.	Visit	Pregnancy test	LVEF	ECG

